#### 7.3.1 Unscheduled visits

In some circumstances a patient may need to return to clinic outside of the suggested follow up visits, for instance due to a disease flare. Patient might also be admitted for severe disease exacerbations. If that is the case, data should be recorded on the eCRF. All data will be collected as if a routine follow up visit but with the addition of:

- Reason for return
- Adverse events
- Safety bloods (only collected if part of the reason for the unscheduled visit)
- Concomitant medications
- Blood pressure (only if part of the reason for the unscheduled visit)
- Outcome of the visit
- Severity assessment (EASI, EASI-50, EASI-75 & IGA, POEM and EQ-5D-5L (adults)/EQ-5D-Y (children)

#### 7.3.2 Early Access Medicine Scheme

Retrospective enrolment of patients will be allowed if they are currently participating in an Early Access Medicine Scheme for a new atopic eczema treatment. All the relevant data that was previously collected for clinical or EAMS purposes will be entered into the eCRF at the appropriate timepoint, and the patient will continue prospective visits as per A-STAR schedule.

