#### **6 STUDY POPULATION**

#### 6.1 Inclusion Criteria

- 1. Paediatric and adult patients with atopic eczema who due to the severity of their disease and/or impact on quality of life are commencing on or switching to another systemic immuno-modulatory agent (e.g. CsA, AZA, MTX or biologic treatments), or who initiated their treatment within the last four weeks and have all required pre-treatment outcomes available.
- 2. Written informed consent for study participation obtained from the patient or parents / legal guardian, with assent as appropriate by the patient, depending on the level of understanding.
- 3. Participants consent to participate in long-term follow up and access to all medical records, including hospital admission records and linkage to data held by NHS bodies or other national providers of healthcare data.
- 4. Diagnosis of atopic eczema in keeping with the UK diagnostic criteria.
- 5. Willingness to comply with all study requirements.
- 6. Competent use of English language, according to patient's age (capable of understanding patient questionnaires).

There is no upper or lower age limit for participation. The decision to start systemic therapy or switch to another systemic agent will be the result of the treating dermatology consultant's decision, following discussion with the patient/parent/legal guardian, without using a pre-specified severity score cut off. It is the treating physician's responsibility to ensure that patients are suitable for the therapy, and that any standard of care treatment or assessments are provided alongside participation in the study as per local requirements.

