In situations when a patient was recruited within the first 4 weeks after treatment initiation, the baseline visit will be recorded retrospectively, and dated as the day of systemic treatment initiation. This can only occur with all required baseline visit data is available to avoid key data missingness.

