#### Treatment safety (pharmacovigilance):

Although we will not have adequate statistical power for a comparative analysis of rare and long-term latent adverse events of the different agents within the confines of this three-year project due to the relatively small patient numbers and short follow-up period, we will still be able to conduct a meaningful descriptive analysis of more common adverse events collected over an at least one-year period for each treatment modality.

The initial analyses will consist of comparisons in baseline status between the individuals in the treatment cohorts. For the purposes of analysis (initially) follow-up time will be censored in both cohorts if there is switching to another class of biologic therapy and censored in the standard therapy group if there is switching to a biologic agent. The adverse events of interest are calculated per person time of follow-up, after the start of therapy.

Sample size of the novel biologics/small molecule exposure group will be largely determined by external factors, including:

- 1) NICE technology assessments and resulting recommendations;
- 2) whether NICE indicates the need for pharmacovigilance and recommends patients are registered in our registry;
- 3) funding of by NHS, and
- 4) uptake by prescribing dermatologists.

The size of the comparison cohort will be more under our control. However, it is difficult to anticipate the magnitude of rate differences for adverse events between the cohorts as patients from all groups are likely to have had prior exposure to immunosuppressive drugs.

Assuming i) the risk of adverse event is proportional to the length of exposure with equal risk per year (note this may not be so), ii) power of 80%, and iii) a significance level of 5%, the following applies:

Annual adverse	Rate ratio	Person years exposure
event rate		per group
1/10,000	2	235,508
1/1000	2	23,590
2/1000	2	11,817
1/100	2	2,321
2/100	2	1,146
4/100	2	551
5/100	2	437
10/100	2	201

For guidance, the estimated risk of certain adverse events are as follows:

Squamous cell carcinoma with ciclosporin use 1 in 320 Non-melanoma skin cancer 1 in 1,000 Melanoma in high dose PUVA (phototherapy) 1 in 1,666 Melanoma in normal person 1 in 10,000

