#### Adverse events/pharmacovigilance:

Drug adverse events are calculated per person time of follow up, after the start of therapy. Time-dependent regression analyses will be undertaken to compare event rates between groups, using standard multivariable analyses to reduce confounding. We will explore the use of other statistical techniques, including propensity score matching, to accommodate confounding by indication. As children and adolescents may have a different phenotype of atopic eczema compared to adults and may respond differently to systemic therapy, we will explore this further in comparative analyses.

Estimating the risk of rare adverse effects with a smaller signal, especially lymphoma will be facilitated by long-term linkage to the national cancer registry (in addition to the control group). The risk window for cancer being defined as once exposed always at risk. Where two biologicals have been used, the proportion of time spent on each will define its possible contribution to risk. Where the adverse event is rare or where a biological intervention is under-represented in the register, the numbers of patient's data can also potentially be increased by sharing data with other compatible registers such as those operating in Germany, Italy, Spain, France, Denmark, and the Netherlands.

The aim in the long-term is to recruit at least 4,000 patients on conventional treatments and also at least 2,000 on each biological intervention (depending on the uptake of these drugs in clinical practice). 4,000 patients in

each cohort, biologicals and conventional treatment would give an exposure of 12,000 patient years in each group. This would give power to detect at least a 3- or 4-fold increase in risk of events occurring at a frequency of 1 in a 1000 or 1 in 2000 patients. Rarer events would be detected if the relative risks were higher.

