# 10.7 Reporting procedures

All adverse events should be recorded from initiation of treatment until withdrawn from study. Depending on the nature of the event the reporting procedures below should be followed. Any questions concerning adverse

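### Patients enrolled retrospectively from an Early Access Medicine Scheme bring immortal time that favours new drugs on drug survival and on fatal or treatment-ending event rates

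*Protocol*

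**What the plan says.** Section 7.3.2 opens a retrospective route for patients on a new drug: "Retrospective enrolment of patients will be allowed if they are currently participating in an Early Access Medicine Scheme for a new atopic eczema treatment". Their history is then back-filled: "All the relevant data that was previously collected for clinical or EAMS purposes will be entered into the eCRF at the appropriate timepoint". No limit is set on how long the patient may already have been treated.

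A second, shorter route in section 6.1 admits patients on any systemic agent "who initiated their treatment within the last four weeks and have all required pre-treatment outcomes available". For these patients section 7.2 says that "the baseline visit will be recorded retrospectively, and dated as the day of systemic treatment initiation".

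The time origin for safety is given twice. Section 9.3 has "The adverse events of interest are calculated per person time of follow-up, after the start of therapy" and section 9.4 has "Drug adverse events are calculated per person time of follow up, after the start of therapy". The outcomes listed in section 2 include drug survival, with time to discontinuation as the example, and section 9.4 assigns Kaplan-Meier methods to it. Section 10.7 adds: "All adverse events should be recorded from initiation of treatment until withdrawn from study".

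The protocol has no rule on delayed entry, left truncation or separate handling of time before enrolment.

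**The concern.** The entry condition and the time origin do not fit together. Entry through the scheme requires the patient to be in it on the day of enrolment, hence alive and presumably still on the drug. If the clock is then set back to the first dose, the patient is credited with time in which death or leaving the scheme could not have been observed, because either would have kept the patient out of the register. That time enters the denominator and can add nothing to the numerator for those outcomes.

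The error is differential. The route exists only for new treatments; azathioprine, ciclosporin and methotrexate have no counterpart. The protocol sets out to compare treatment groups on adverse events (section 9.2, item 4) and on drug survival (section 9.4). New drugs would therefore look safer for fatal and treatment-ending events, and more persistent, than they are. A larger register does not reduce this bias.

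**Working it through.** **Inputs from the protocol**
- Safety power table (9.3): rate ratio 2, 80% power, 5% significance; 2,321 person-years per group at an annual rate of 1/100.
- Long-term exposure (9.4): 12,000 patient-years from 4,000 patients per group.
- Lag on the short route (6.1): at most 4 weeks.

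**Inputs the protocol does not give (assumed, shown as ranges)**
- Share of a drug's cohort entering through the scheme, s: 10% to 100%.
- Lag from first dose to enrolment, L: 3 to 12 months.
- True 12-month drug survival: 80%, constant hazard.

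**Step 1. The plan's own figures.** 12,000 / 4,000 gives a mean follow-up T of 3 years. The power table is reproduced by the two-sided two-proportion formula with pooled variance and no continuity correction:

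n = [z(0.975)·√(2p̄(1−p̄)) + z(0.80)·√(p1(1−p1) + p2(1−p2))]² / (p1−p2)²

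| Annual rate | Stated | Recomputed |
|---|---|---|
| 1/10,000 | 235,508 | 235,430 |
| 1/1,000 | 23,590 | 23,511 |
| 2/1,000 | 11,817 | 11,737 |
| 1/100 | 2,321 | 2,319 |
| 2/100 | 1,146 | 1,141 |
| 4/100 | 551 | 553 |
| 5/100 | 437 | 435 |
| 10/100 | 201 | 199 |

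All eight rows agree within 1%. The table stands; what changes is the exposure that may be counted against it.

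**Step 2. Effect on event rates.** Let the true rate be λ. In the worst case no event is captured during the lag. Expected events per patient are λ(T − sL), but the time counted is T, so

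observed rate = λ(1 − sL/T).

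This worst case is apt for deaths and for events that end treatment or scheme participation. For other events it is an upper bound. With T = 3 years and a true rate ratio of 2 (new drug against conventional, conventional rate 1/100):

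| s | L | 1 − sL/T | Ratio 2 reads | Power at 2,321 person-years |
|---|---|---|---|---|
| 10% | 3 months | 0.992 | 1.98 | not computed |
| 50% | 6 months | 0.917 | 1.83 | 67% |
| 100% | 6 months | 0.833 | 1.67 | 51% |
| 100% | 12 months | 0.667 | 1.33 | 18% |

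The planned power is 80%.

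**Step 3. Effect on drug survival.** If entry at L requires being on the drug at L, and the clock runs from first dose, the curve at 12 months reads S(12)/S(L). With S(12) = 0.80 and constant hazard, S(6 months) = √0.80 = 0.894, so an all-scheme cohort reads 0.80/0.894 = 89.4%. With a 3-month lag it reads 84.6%. If half of those enrolled came through the scheme at 6 months: 0.5 × 80% + 0.5 × 89.4% = 84.7%. If a tenth did: 0.9 × 80% + 0.1 × 89.4% = 80.9%.

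**Step 4. The 4-week route.** If every patient used it at the maximum lag, the share of person-time involved is (4/52)/3 = 2.6% at 3 years, or 7.7% at 1 year. At 3 years a true ratio of 2 would read 1.95 if only the new-drug group were affected.

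**Step 5. After delayed entry.** Counting time from consent gives λ(T − sL)/(T − sL) = λ, provided that patients who enter have the same later risk as those who started when they did and stayed in the scheme. Countable exposure becomes 12,000 × (1 − 0.5 × 0.5/3) = 11,000 patient-years at a 50% share and 6-month lag, and 10,000 at 100%. If instead all patients used the 4-week route, 11,692 would remain.

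**The case against.** The strongest reply is that the protocol never says outright that the lag is counted. Person-time of follow-up beginning with therapy could mean observed follow-up restricted to time on or after first dose. That restriction has an ordinary purpose, since baseline may precede treatment by up to 28 days. Risk-set entry is often left to the SAP, which is not at hand. This stands in part: counting scheme time from first dose is an inference. But it is the natural reading when earlier data are placed at their original timepoints and the rate clock is tied to therapy start, and an SAP using delayed entry would have to qualify what sections 9.3 and 9.4 state.

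The second reply is that earlier adverse events are captured: section 7.3.2 back-fills data and section 10.7 has events recorded from treatment initiation. This stands for non-fatal events that did not end treatment, which then have both numerator and denominator. What remains for them is selection of patients who tolerate the drug, and under-recording before enrolment.

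A reader might go further than the document allows in three ways:
- **The 4-week route also flatters new drugs.** Sections 6.1 and 7.1 open it to every systemic agent and do not require the patient to be still on treatment. It is small and not differential by rule.
- **Baseline assessment dates are overwritten.** Section 7.2 dates the visit, for the 4-week route only. It does not say that the dates of the underlying assessments are lost.
- **Scheme patients must be dropped from the primary EASI comparison.** That endpoint is not a person-time measure, and the protocol does not show that any drug compared there came through a scheme. A patient enrolled after V3 does contribute V3 data only because they stayed in the scheme, which justifies a sensitivity analysis and no more.

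**Conclusion.** The point holds for the early-access route. As written, the protocol combines entry conditional on still being in the scheme, an unlimited lag, and a clock tied to first dose, with no delayed entry. Pre-enrolment time is then immortal for death and for events that end treatment or scheme participation, for new drugs only. The direction is clear: higher drug survival and lower rates of those events relative to conventional drugs.

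The size is open. It depends on share, lag and follow-up, none of which is fixed for these patients. At 3 years it runs from negligible (factor 0.992) to material (0.833 or lower), and the larger figures need a whole cohort entering through the scheme. It would be wrong to infer that serious-event rates in general are halved: at a 6-month lag that needs a 100% share, only 12 months of follow-up and no capture of earlier events. The drug-survival figures also assume that being in the scheme means being on the drug, and a constant hazard.

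**What to change.** In sections 9.3 and 9.4, state that for patients enrolled retrospectively, through an early-access scheme or the 4-week route, at-risk time starts at the later of therapy start and first A-STAR consent (left truncation). Apply this to event rates, the time-dependent regression and Kaplan-Meier drug survival. Use the first consent, not the re-consent at transfer (7.4.1) or at age 16 (11.3.1).

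Keep recording events before consent and report them descriptively, but leave them out of the rates. Add a sensitivity analysis that excludes retrospectively enrolled early-access episodes, including from the V3 EASI comparison. Report the number of such episodes and the distribution of their lag by drug, so that the size of the issue can be seen.

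The cost is wording and use of the consent date, which is on the signed form. Countable exposure falls somewhat, for example from 12,000 to 11,000 patient-years at a 50% share and 6-month lag. For a drug whose patients nearly all entered late, few are at risk in the first months, so the early part of its drug-survival curve will be imprecise, or will have to be read as conditional on having reached the earliest entry time. No change to clinical management is involved.

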#### 7 ENROLMENT

## 7.1 Recruitment and screening

Participants will be identified by the clinical team at each centre, most likely from their regular outpatient clinics. If deemed suitable for prescribing of a new systemic immuno-modulatory treatment, or if the patient has been prescribed a new systemic medication within the last 4 weeks and their pre-treatment outcomes are available, the patient and/or their parent/guardian will be asked if they are willing to participate in the study. A Patient Information Sheet and instructions on how to proceed if they are interested in taking part or finding out more about the study will be given to the patient and/or parent/guardian. They will be provided with the contact details to contact the research nurse if they wish to discuss or need further information. All patients and/or parent/guardian will be provided with a full explanation of the study, before obtaining informed written consent.

Patients can also self-refer to the study (using the details found on the study website or recruitment poster).

The time taken from initial contact and provision of information to obtaining written consent should be sufficient to enable appropriate discussions with the patient / family about the study, explanation of the protocol and procedures.

A patient and/or parent/legal guardian should be provided with the study information during their outpatient appointment and may be approached for consent during this visit if considered appropriate. Where the patient and/or parent/legal guardian feel that they have had adequate time to consider, enough information regarding the study and are happy to proceed, then consent can be sought and screening assessments can be undertaken on the same day as initial contact and provision of information.

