Patients will be followed up for as long as possible, even if they stop treatment. The following target visit windows apply: V2 + /-2 weeks (weeks 2-6), and then +/-4 weeks thereafter, i.e. V3 weeks 12-20, etc. The date of the actual visit will be recorded in the CRF. For patients participating in the bioresource, the target visit windows are reduced to: V2 + /-1 week and V3 + /-1 week with +/-2 weeks in exceptional circumstances.

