#### 9 STATISTICAL CONSIDERATIONS

## 9.1 Primary endpoints

Change in disease severity between baseline and three months into treatment (V3), comparing the different treatment modalities with each other, using the EASI (Eczema Area and Severity Index).

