## 9.4 Statistical analyses

#### Treatment effectiveness:

Descriptive statistics, t-tests, regression and Kaplan-Meier survival analyses will be applied as appropriate to examine treatment effectiveness between drugs, adverse events, drug cost/QALY, and drug survival respectively. Primary treatment effectiveness variables are the mean EASI score, corrected for baseline scores. We will also compare the proportion of patients with an EASI reduction of 50%. For the purposes of analysis, follow up time will be censored in both cohorts if there is switching to another class of therapy and censored in the standard therapy cohort if there is switching to another systemic agent.

The potential effect of *FLG* genotype on treatment response:

In addition to the above analyses, we will conduct a subgroup analysis to investigate whether *FLG* genotype stratifies with treatment response, as *FLG* genotype is potentially an important biomarker but has not been investigated in the context of conventional systemic therapy for atopic eczema. We hypothesise that those with one or more *FLG* loss-of-function mutation(s) respond less well to therapy, as has been seen for the biologic treatment omalizumab [26]. Based on the available literature for patients with moderate-to-severe atopic eczema, we expect 40% of our participants to carry one or more *FLG* loss-of-function mutations. Under these assumptions, all treatment comparisons (AZA vs CsA, AZA vs MTX, CsA vs MTX, dupilumab vs any of the standard systemic medications) are able to detect an effect size as low as 20% difference in treatment responses that are close to the expected MCID\* (=MCID x 80%) with 80% power. Further detail on the differences that can be detected are shown below alongside the expected MCIDs (MCID\*).

The following assumptions are made in these calculations:

- -Available sample sizes are Azathioprine (AZA): 32, Ciclosporin (CsA): 28, Methotrexate (MTX): 20, Dupilumab (Dup): 40 (expecting 40% of our study participants to carry a *FLG* mutation).
- -MCID and corresponding standard deviation is for children and adults combined and reduced by 20% to 5.3.
- -The analysis will use a 2-sample t-test to look at change in score (for the purposes of checking the sample size). The actual analysis will test interactions and therefore have lower statistical power.
- -A 5% significance level (2-sided) will be used.

	EASI score			
Comparison	Difference	Comparison	Difference	MCID*

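### Section 7.3.2 lets Early Access Medicine Scheme patients enter late without a required pre-treatment EASI, against the entry limits in 6.1, 7.1 and 7.2, so the primary EASI change is not assured for these new-drug patients

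*Protocol*

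**What the plan says.** The protocol has two routes for a patient who has already started treatment.

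**Four-week route.** Inclusion criterion 1 (6.1) covers patients starting or switching treatment, "or who initiated their treatment within the last four weeks and have all required pre-treatment outcomes available". Section 7.1 repeats both conditions: "if the patient has been prescribed a new systemic medication within the last 4 weeks and their pre-treatment outcomes are available". For patients recruited this way, 7.2 has the baseline visit recorded after the fact and adds: "This can only occur with all required baseline visit data is available to avoid key data missingness".

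**EAMS route.** Section 7.3.2 states: "Retrospective enrolment of patients will be allowed if they are currently participating in an Early Access Medicine Scheme for a new atopic eczema treatment". Its data requirement is "All the relevant data that was previously collected for clinical or EAMS purposes will be entered into the eCRF at the appropriate timepoint", after which prospective visits follow the usual schedule.

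**What the data are for.** The primary endpoint in 9.1 is "Change in disease severity between baseline and three months into treatment (V3), comparing the different treatment modalities with each other", measured with EASI. Section 9.4 adds: "Primary treatment effectiveness variables are the mean EASI score, corrected for baseline scores". Section 7.3 gives the V3 window as "and then +/-4 weeks thereafter, i.e. V3 weeks 12-20, etc".

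**The concern.** The two routes do not agree. An EAMS patient ten weeks into treatment, or one without a complete baseline, is admitted by 7.3.2 but fails criterion 1 as written. A site cannot tell which rule governs.

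The statistical stake is in the comparison between drugs. The protocol protects the baseline for the four-week route and says why: to keep key data from being missing. It has no such protection for the EAMS route. Those patients are by definition on a new treatment, so a missing or selectively available primary outcome would arise on one side of the comparison only. Correcting for baseline cannot help where no baseline exists.

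**Working it through.** No figure in the protocol bears on this point, so the check sets the sections side by side.

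| | 6.1 criterion 1 and 7.1 | 7.2 | 7.3.2 |
|---|---|---|---|
| Who | Already-treated patients | Patients recruited in the first four weeks | Patients currently in an EAMS |
| Maximum time since start | Four weeks | Four weeks | None stated |
| Pre-treatment data | Outcomes must be available | All required baseline data | Relevant data already collected; no minimum set |
| EAMS mentioned | No | No | Yes, without reference to 6.1, 7.1 or 7.2 |

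**Step 1: what the endpoint needs.** The change in 9.1 and the baseline correction in 9.4 need an EASI before treatment and another in the V3 window, weeks 12 to 20. The EASI changes in 9.2 and the 50% reduction in 9.4 need the same baseline.

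**Step 2: what each route guarantees.** A four-week entrant has a baseline by rule, and V3 still lies ahead, since week 4 precedes week 12. For an EAMS entrant:

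- enrolled before week 12, V3 can be collected prospectively, but the baseline depends on what was recorded earlier;
- enrolled after week 20, both the baseline and the V3 value depend on what was recorded earlier.

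Section 7.3.2 requires neither value to exist.

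**Step 3: who can enter late.** Entry requires current participation in the scheme. A patient who started the new drug and left the scheme at week 8 cannot be enrolled by this route at week 30; one who stayed in it can. Patients enrolled at or near treatment start are treated differently. Under 7.4.2, stopping therapy is no reason to leave follow-up, so their early stoppers remain in the register, subject to the censoring at a switch in 9.4. Late EAMS entrants are therefore conditioned on persistence, and the comparison groups are not. If patients who leave early tend to have responded less well, which is an assumption, this favours the new drug.

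**Step 4: which groups are affected.** The EAMS route exists only for a new atopic eczema treatment, so Steps 2 and 3 apply to new-drug groups alone.

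**The case against.** The strongest reply is that 7.3.2 is a specific permission under its own heading and reads naturally as a deliberate exception to a general rule. That stands as far as it goes. On that reading the clash over who may enrol becomes a missing cross-reference. It does not restore the baseline safeguard, and it confirms that the safeguard is absent for one class of drug only.

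Three further replies also carry weight.

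- The full-baseline sentence in 7.2 is tied to the four-week route and does not say that all entry must fall within four weeks. That is correct. The time limit comes from 6.1 and 7.1.
- Handling of missing baselines and definition of analysis sets are commonly left to the SAP. That is fair, and the absence of a missing-data rule is not counted here. The entry conditions are a protocol matter, however, and no later analysis plan can supply a pre-treatment EASI that was never required.
- Section 7.3.2 asks for all relevant earlier data to be placed at the right visit, which may well include EASI at baseline and week 16. That is also fair.

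A reader might go further and infer that these patients may enter at any time with any data, that their endpoint cannot be computed, or that power is materially reduced. The protocol does not support this. Entry requires current scheme participation. Nothing shows that any EAMS patient lacks an EASI. No EAMS share is given from which to compute a power loss. The printed detectable differences against dupilumab (3.2 to 3.7) are also well below the stated MCID of 6.6, so selection matters more here than power.

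**Conclusion.** The concern holds in a limited form. The entry rules in 6.1 and 7.1, with the baseline condition in 7.2, are not reconciled with 7.3.2. As written, the protocol does not ensure that the primary EASI change can be scored for EAMS entrants, and it lets late entrants into the primary comparison selected on still being in the scheme. Both effects are confined to new-drug groups.

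The size cannot be stated, because the protocol gives neither the number of EAMS patients nor the fraction with an EASI at the needed times. If few are enrolled, or all have dated assessments, the scoring problem is negligible. The selection of late entrants would remain even with complete data. The direction of that bias rests on the assumption that those who leave a scheme early tend to do worse.

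**What to change.** 1. In 6.1 (criterion 1) and 7.1, name EAMS patients as an exception to the four-week limit. In 7.2, state what baseline data the EAMS route needs, with a cross-reference to 7.3.2.
2. In 7.3.2 and Section 9, count an EAMS patient in the 9.1 and 9.2 effectiveness comparisons only if an EASI dated before the first dose is in the eCRF. Since 7.2 dates a retrospective baseline visit to the day treatment started, record the actual assessment date as well.
3. Keep EAMS patients enrolled after the V3 window (week 20) out of the primary comparison. Where both a pre-dose EASI and an in-window V3 EASI exist, they may enter a sensitivity analysis. The reason is selection on remaining in the scheme, not a lack of data.
4. Keep all EAMS patients in the register for safety and later follow-up. Report separately, by drug, how many were left out of the effectiveness comparisons under points 2 and 3.

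The cost is a few sentences of protocol wording and one date field if it is not already captured. Some EAMS patients leave the primary effectiveness set, which makes the new-drug group smaller there; none leaves the register.
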